13.1. Populations for Analysis

The following analysis populations are planned for this study:

- Safety population: all patients who receive at least one dose of the investigational product. All safety analyses will be performed using this population, analyzed as treated.
- Intention-to-Treat (ITT) population: all patients who are randomized. This is the primary population for efficacy analyses, and patients will be analyzed based on their randomized treatment.

13.2. Estimate of Sample Size

The study is planned to enroll approximately 470 patients total in a 1:1 randomization, that is, 235 patients in each of the TNX-102 SL 5.6 mg and placebo arms. [REDACTED]

13.3. Assessment of Demographic and Baseline Characteristics

Demographic and baseline characteristics such as age, gender, race/ethnicity, height, weight, BMI, family status, education, employment status, smoking history, MINI modules (A, C, I, J, K) diagnoses, and 2016 Revised 2010/2011 FM Diagnostic criteria will be summarized by treatment group (TNX-102 SL and placebo) and overall using descriptive statistics.

Medical History will be coded using the Medical Dictionary for Regulatory Activities (MedDRA)[®] and summarized by System Organ Class (SOC) and Preferred Term using frequency counts by treatment group.

13.4. Efficacy Analyses

13.4.1. Efficacy Endpoints

Primary Efficacy Endpoint:

- Change from Baseline to the Week 14 endpoint in the diary NRS weekly average of daily self-reported average pain severity scores.

Secondary Efficacy Endpoints:

The six secondary efficacy endpoints listed below are considered key secondary endpoints and will be tested in that order:

- Proportion of patients with a PGIC rating of “very much improved” or “much improved” at the Week 14 endpoint
- Change from baseline in the FIQR symptoms domain score at the Week 14 endpoint
- Change from baseline in the FIQR function domain score at the Week 14 endpoint
- Change from baseline in the PROMIS score for sleep disturbance at the Week 14 endpoint
- Change from baseline in the PROMIS score for fatigue at the Week 14 endpoint
- Change from baseline in the weekly average of the daily diary assessment of sleep quality at the Week 14 endpoint

Exploratory efficacy endpoints:

- Proportion of patients with a $\geq 30\%$ improvement from baseline to Weeks 1-14 in the daily self-reported average pain severity score
- Proportion of patients with a $\geq 50\%$ improvement from baseline to Weeks 1-14 in the daily self-reported average pain severity scores
- Proportion of patients with a PGIC rating of “very much improved” or “much improved” at all post-randomization clinic visits
- Change from baseline in the FIQR total score, overall impact domain score, and individual item scores at all post-randomization clinic visits
- Change from baseline in the FIQR symptoms domain score and function domain scores at all post-randomization clinic visits
- Change from baseline in the PROMIS score for sleep disturbance at all post-randomization clinic visits
- Change from baseline in the PROMIS score for fatigue at all post-randomization clinic visits
- Change from baseline in the weekly average of the daily diary assessment of sleep quality at Weeks 1-14
- Change from baseline in the weekly average of the daily self-reported average pain severity scores at Weeks 1-14
- Changes from baseline in patient-rated Changes in Sexual Functioning Questionnaire Short-Form (CSFQ-14) in females and in males, analyzed separately

13.4.2. Primary Efficacy Analysis

The primary efficacy parameter will be the contrast between active and placebo in the weekly mean change from baseline pain score at the Week 14 endpoint. The weekly pain score will be

based on the weekly average of the daily patient self-reported 24-hour recall average pain severity scores using an 11-point (0-10) NRS.

The primary ITT analysis will provide an estimate of the following causal estimand for the primary analysis: the difference in the weekly mean change from Baseline of the daily patient self-reported 24-hour recall average pain severity rating using an 11-point (0-10) NRS evaluated at the Week 14 endpoint in all randomized patients attributable to the initially randomized treatment assignment.

The primary analysis will use a MMRM approach with multiple imputation for missing data. Covariates in the model will include the fixed categorical effects of treatment, center, study week, and treatment by study week interaction, as well as the continuous fixed covariates of baseline score and baseline score by study week interaction. Please see the separate SAP for more details on the primary and secondary analyses.

13.4.3. Sensitivity Analyses

The primary analysis will be followed by several sensitivity analyses. The SAP will include full details of the sensitivity analyses planned for this study.

13.4.4. Secondary Efficacy Analyses

Secondary efficacy analyses will be based on the ITT population only. For PGIC, patients with a “very much improved” or “much improved” response at the Week 14 endpoint will be considered responders. Patients with results in any other category or who discontinue early will be considered non-responders. PGIC responder status (yes/no) will be analysed using logistic regression with treatment and site as categorical effects. In addition, odds ratios and corresponding 95% confidence intervals will be presented.

Analysis of continuous secondary endpoints and adjustments for missing data will be described in detail in the SAP. Significance tests of treatment differences will be tested at the two-sided 0.05 level and corresponding 95% confidence intervals will be calculated.

To adjust for multiplicity and to control for overall type I error, a sequential test procedure will be applied to the efficacy endpoints. If the primary analysis produces a result that is statistically significant at the 0.05 level, a significance level of 0.05 will be used for comparing the secondary endpoints in an ordered fashion. If the analysis for a secondary endpoint does not produce a statistically significant result at the 0.05 level, then the remaining secondary endpoint analyses will automatically be considered non-significant regardless of the p-value produced. The order in which the secondary endpoints are to be tested will be specified in the SAP.

No other adjustments for multiplicity will be made and other p-values displayed in the output will be considered for descriptive summary purposes only and will not be used for formal inference. Full details regarding the statistical analyses for the listed endpoints, including graphical presentations, can be found in the SAP.

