13. STATISTICAL CONSIDERATIONS AND ANALYSES

A complete description of the statistical analyses to be performed will be provided in the study-specific SAP, which will be finalized prior to database lock and the unblinding of study treatments.

Baseline will be defined as those values recorded closest to, but prior to administration of the first dose of study drug.

Unless otherwise noted, significance tests of treatment differences will be tested at the two-sided 0.05 level.

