13.6. Interim Analyses

An interim analysis will be performed once 50% of the planned patients have enrolled and those patients have either completed or discontinued the study. The purpose of the interim will be to potentially increase the sample size to maintain statistical power conditioned on the results of the first 50% of patients; or continue as planned if conditional probability of success at Week 14 is above a pre-specified threshold; or to stop the study early for success or for futility if the conditional power is sufficiently low. The study team will only be informed of the recommendation to maintain the original sample size, increase the sample size (by a fixed, pre-specified amount) or discontinue the study for success or for failure (at which point unblinding would occur).

For the primary and key secondary outcomes, the results from before and after the interim will be combined with Cui, Hung, Wang (CHW) methodology (Cui et al, 1999). Full details of the interim analysis will be included in the SAP and finalized prior to execution of the interim analysis.

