8.1.1 Adjustments for Multiplicity and Other Alpha Control

8.1.1.1 Alpha Spend, Early Stops and Sample Size Increase

[REDACTED]

Under both cases (early stop for efficacy, study continues to full enrollment), the alpha adjustment being applied to the primary will also be utilized as the criteria for the key secondary outcomes.

Likewise, in the case of a sample size increase, the same inverse-normal method described in the primary efficacy analysis will be applied to the key secondary analyses to adjust the reported p-value; these will be tested with the adjusted alpha to account for the first stage alpha spend.

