The mean change from baseline in the weekly average of daily pain scores from baseline to each week in the TNX-102 SL and placebo arms will be analyzed using a restricted maximum likelihood (REML) based repeated measures approach with data imputed using multiple imputation (see [Section 8.1.3](#)). Week 14 will serve as the primary time point of interest. Models will be run on each of the twenty imputation sets individually and will include the fixed, categorical effects of treatment, site, study week, and treatment by study week interaction, as well as the fixed covariates of baseline value and baseline value score-by-study week interaction. An unstructured covariance structure will be used to model the within-subject errors. If this analysis fails to converge, the following structures will be tested in this order: first order ante dependence, heterogeneous first order autoregressive, heterogeneous compound symmetry and compound symmetry with the first to give convergence used. The Kenward-Roger approximation will be used to estimate the denominator degrees of freedom. LS means and differences across the twenty MI reps will be combined using SAS procedure MIANALYZE ([Rubin, 1976](#)). Significance testing will be based on least-squares means and two-sided 95% confidence intervals will be presented. [REDACTED]

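### Protocol 13.4.4 sets the final primary and key secondary tests at the full 0.05 despite a possible early stop for success, while SAP 8.1.1.1 uses an alpha reduced for the first-stage spend; the two need reconciling

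*Protocol*

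**What the plan says.** **Protocol.** The general rule in section 13, subject to exceptions noted elsewhere, is that "significance tests of treatment differences will be tested at the two-sided 0.05 level". Section 13.4.4 then sets the gate for the testing sequence: "If the primary analysis produces a result that is statistically significant at the 0.05 level, a significance level of 0.05 will be used" for the ordered secondaries. It presents this sequence as the means of controlling overall type I error. On intervals the same section says: "Significance tests of treatment differences will be tested at the two-sided 0.05 level and corresponding 95% confidence intervals will be calculated". Section 13.6 adds the interim: "An interim analysis will be performed once 50% of the planned patients have enrolled", with options that include "or to stop the study early for success or for futility if the conditional power is sufficiently low". It names the CHW combination of the two stages, gives no alpha spend, and leaves the interim details to the SAP.

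**SAP.** Section 8.1.1.1 applies the primary's alpha adjustment to the key secondaries, both after an early efficacy stop and at full enrolment. For a sample size increase it says of the key secondaries that "these will be tested with the adjusted alpha to account for the first stage alpha spend". Section 8.1.1.2 gives the same fixed sequence as the protocol, with the level blacked out. Section 10.1.2 fixes the stage weights at the square root of 0.5 and says that "two-sided 95% confidence intervals will be presented"; the text directly after that is redacted. Section 5.1 calls the interim optional. Section 13 lists one departure from the protocol, the added in-clinic pain endpoint.

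**The concern.** A level adjusted for alpha already spent must lie below 0.05. The two governing documents therefore give different thresholds for the same decision. The threshold matters beyond the primary endpoint, because the fixed sequence opens or closes all six key secondaries on the primary result. With a p-value in the gap, a reader of the protocol would declare success and go down the list, while a reader of the SAP would stop.

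The protocol's figure also does not by itself deliver the error control that 13.4.4 claims. CHW weighting with fixed weights protects the error rate against a data-driven change of sample size. It does not pay for a chance to reject at the interim. SAP 8.1.1.1 treats these as two separate matters: the combination test, and in addition the adjusted alpha.

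**Working it through.** **Inputs.** From the documents: final two-sided level 0.05 (Protocol 13.4.4); efficacy stop allowed at 50% (Protocol 13.6); weights sqrt(0.5) for each stage (SAP 10.1.2). The interim efficacy level is redacted, so a range is assumed. No credit is given for futility stopping in steps 1 to 3.

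**Step 1: the protocol's own figure.** With a single look, 2 × (1 − Φ(1.960)) = 0.0500. The stated 0.05 is exact if no interim efficacy test is done.

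**Step 2: overall error with one efficacy look and a final test at 0.05.** Under the null, let Z1 be the stage 1 statistic, Y the independent stage 2 statistic, and Z = sqrt(0.5)·Z1 + sqrt(0.5)·Y. With interim level a1 and critical value c1:

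overall alpha = a1 + P(|Z1| ≤ c1 and |Z| > 1.960).

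For a1 = 0.00305, c1 = 2.963 and the second term is 0.0479, so the total is 0.0031 + 0.0479 = 0.0510. For a1 = 0.0294, c1 = 2.178 and the second term is 0.0380, so the total is 0.0294 + 0.0380 = 0.0674.

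**Step 3: the final level that keeps the total at 0.05.** Replace 1.960 by c2 and solve a1 + P(|Z1| ≤ c1 and |Z| > c2) = 0.05.

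| Assumed interim level (two-sided) | Overall alpha, final test at 0.05 | Final level for a total of 0.05 | Matching interval | Width relative to 95% |
|---|---|---|---|---|
| 0.001 | 0.0502 | 0.0498 | 95.02% | 1.001 |
| 0.00305 (Lan-DeMets, O'Brien-Fleming type) | 0.0510 | 0.0490 | 95.10% | 1.004 |
| 0.0052 (classical O'Brien-Fleming) | 0.0520 | 0.0480 | 95.20% | 1.009 |
| 0.01 | 0.0546 | 0.0452 | 95.48% | 1.022 |
| 0.0294 (Pocock) | 0.0674 | 0.0294 | 97.06% | 1.111 |

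The p-values on which the documents disagree run from the third column up to 0.05: 0.049 to 0.05 in the second row, 0.029 to 0.05 in the last.

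**Step 4: how far futility could change this.** Suppose a binding stop when conditional power under the current trend is below 5%, with the final critical value at 1.960. That corresponds to Z1 below about 0.56. With a1 = 0.00305 and the final test at 0.05, the overall alpha falls to 0.047. With a1 = 0.0294 the same rule leaves 0.064. So a binding rule can remove the excess for a conservative interim level, but need not do so for a liberal one.

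**The case against.** The strongest reply is that the SAP already handles this. It prescribes adjusted testing, the protocol hands interim details and the full analysis description to the SAP, and the general rule in Protocol 13 allows for exceptions. An analyst who follows the SAP makes no error, and supplying delegated detail is arguably not a change that section 13 of the SAP must declare.

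Much of that stands, and it is why the remedy is only a wording change. It does not remove the contradiction. Section 13.4.4 carries no reservation of its own on the level and states 0.05 as the gate. It leaves the order of the secondaries and other analysis details to the SAP, but not the threshold.

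Two stronger readings are tempting and are not supported.

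- A reader might infer that the trial's type I error exceeds 5%. The documents do not show this. The interim level is redacted; the futility threshold, and whether it is binding, are not visible, and step 4 shows that a binding rule can offset the excess. The SAP calls the interim optional, whereas the protocol says that it will be done. The SAP also prescribes the adjusted level.
- A reader might infer that the SAP's 95% intervals contradict its test, so that an interval excluding zero could sit beside a failed test. That could happen, because the intervals are described for the least-squares means and not for the two-stage combination at the adjusted level. But text directly after the interval sentence in 10.1.2 and at the start of 8.1.1.1 is redacted and could contain an adjusted interval. The intervals are also for presentation and are not the decision rule. Requiring an interval inverted from the CHW statistic for every endpoint would be more than is needed.

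**Conclusion.** The inconsistency is real and lies in the visible text: Protocol 13.4.4 gives 0.05, SAP 8.1.1.1 gives a lower adjusted level, and SAP section 13 is silent. Its size cannot be fixed because the SAP's levels are redacted. If the efficacy look takes place and futility is non-binding, the protocol's rule gives an overall error of about 5.1% at an assumed interim level of 0.003 and up to about 6.7% at a Pocock-type level. Nothing visible points to the Pocock end of that range. If no efficacy look takes place, 0.05 is exact. The disagreement over p-values between the adjusted level and 0.05 does not depend on the futility rule. It should be corrected, because the success threshold of a Phase 3 trial should read the same in both documents. The interval question is secondary and conditional on the redacted text.

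**What to change.** - In Protocol 13.4.4, and for these tests in the general statement in Protocol 13, replace 0.05 by a reference to the adjusted two-sided alpha given in SAP 8.1.1.
- List this in SAP section 13 as a difference from the protocol.
- Unless the redacted text already does so, state in SAP 10.1.2 and 10.2 that the 95% intervals are nominal, or give the interval at the adjusted level beside them.

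This needs no new data and no change of design. The cost is a few sentences, at most one further interval per endpoint, and a stated threshold slightly less favourable than 0.05.

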13.4.5. Exploratory Efficacy Analyses

Exploratory efficacy analyses will be based on the ITT population. Details on exploratory efficacy analyses can be found in the SAP.

13.5. Safety Analyses

Safety analyses will be performed using the Safety Population. The analysis of safety assessments in this study will include summaries of the following safety and tolerability data collected for each patient:

- Incidence of Adverse Events
- Changes from baseline in clinical laboratory tests
- Changes from baseline in vital signs
- Changes from baseline in physical examination findings including examination of the oral cavity
- Monitoring suicidality using the C-SSRS
- Changes from baseline in BDI-II scores

All AEs, treatment-emergent adverse events (TEAE), and serious adverse events (SAE) will be coded using the MedDRA.

An AE summary table will be presented for the following:

- All TEAEs
- TEAEs by severity
- TEAEs leading to study drug discontinuation
- TEAEs by relationship
- SAEs
- Oral cavity TEAEs
- Oral cavity TEAEs by severity

Summaries of incidence rates (frequencies and percentages), of individual AEs by MedDRA SOC and preferred term will be prepared. Such summaries will be displayed for all TEAEs, oral cavity TEAEs, TEAEs by maximum severity, and TEAEs by strongest relationship to study drug.

Each patient will be counted only once within each summation level (SOC; preferred term). If a patient experiences more than one TEAE within each summation level, the TEAE with the strongest relationship or the maximum severity, as appropriate, will be included in the summaries of relationship and severity.

In the AE data listings, all AEs will be displayed.

Laboratory data include analytes for Chemistry and Hematology, and these will be summarized by treatment and visit for the Safety Population. Descriptive summaries of actual values and changes from baseline will be presented by study visit and last on-treatment assessment for each clinical laboratory analyte and each treatment group. 95% confidence intervals will be presented for change from baseline.

Laboratory values will be displayed in the data listings with their corresponding normal ranges, and those values that are outside the normal range will be flagged. For each laboratory analyte, shifts in assessments of abnormality from baseline to each scheduled time point will be presented in shift tables.

A by-patient listing of all clinical laboratory data will also be provided.

Descriptive summaries (mean, SD, median, minimum, and maximum) of actual values and changes from baseline at each assessment time point and last on-treatment assessment will be calculated for vital signs including weight, BMI, body temperature, pulse rate, systolic blood pressure and diastolic blood pressure. 95% confidence intervals will be presented for change from baseline.

Based on the C-SSRS results, the overall number of patients with lifetime and/or current suicidal ideation (by item and category), suicidal behavior (by item and category), or self-injurious behavior at the screening and baseline visit will be summarized by visit and treatment group. Additionally, the overall number of patients with any suicidal ideation or behavior (by type and in total) or self-injurious behavior while on-treatment will be provided by treatment group. Patients will only be counted once for on-treatment at the worst-case response for each item.

Physical examination data and oral examination data will be presented in data listings.

Descriptive summaries (mean, SD, median, minimum, and maximum) of actual values and changes from baseline at each assessment time point and last on-treatment assessment will be calculated for BDI-II scores. 95% confidence intervals will be presented for change from baseline.

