7.2.4. Safety

- Incidence of adverse events
- Changes from baseline in clinical laboratory tests
- Changes from baseline in vital signs
- Assessment of physical examination findings including examinations of the oral cavity
- Monitoring suicidality using the Columbia- Suicide Severity Rating Scale (C-SSRS) scale
- Changes from baseline in Beck Depression Inventory-II (BDI-II) scores

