11.2.2. Baseline Visit

For patients who have qualified for randomization, these assessments and procedures will be completed in the following general order:

- Confirm patient's eligibility based on the diary data collected during the preceding 7 days
- Review completed diary data with the patient
- Update medical history (with any changes noted since screening)
- Assess changes in medication history and concomitant medications
- Have the patient complete the BDI-II. If the BDI score is >24 , the patient is not eligible for randomization and should be screen failed. In addition, a score > 1 on item #9 (suicidal ideation) is exclusionary.
- Administer the "Since Last Visit" version of the C-SSRS. Any patient exhibiting Type 3, 4, or 5 suicidal ideation or any suicidal behavior since the Screening visit should be screen-failed and assessed for appropriate follow-up care.
 - a. Results of the C-SSRS and BDI-II should be reviewed together to ensure (1) the patient is not experiencing suicidal ideation or worsening depression that requires intervention and (2) both scales are providing a consistent clinical picture of the patient with regard to suicidality.
- Assess occurrence of adverse events
- Conduct a brief physical examination, including vital signs and weight
- Conduct a visual examination of the oral cavity. This examination should include a careful visual examination of the sublingual area, tongue, buccal mucosa, lips, palate and gums. Any abnormalities should be noted on the oral exam source document. It is recommended that both non-significant as well as significant findings be noted so that there is a complete and accurate baseline assessment available for comparison to findings at later visits.
- Perform urine pregnancy test (for women of child-bearing potential)
- Patient should complete the following patient-reported outcomes (PRO):
 - a. FIQR
 - b. Clinic administered assessment of pain by both 24-hour and weekly recall using 11-point (0-10) NRS scale
 - c. PROMIS scales for sleep disturbance and fatigue
 - d. CSFQ-14 female or male version, as appropriate
- Ensure that all PROs were accurately and fully completed

- Once it has been confirmed that the patient remains eligible, randomize patient via IRT Randomization System
- Dispense bottle of double-blind study drug as assigned via the IRT
- Review patient instructions regarding study drug dosing and diary completion (Section 10.2 and Section 12.2.6).

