11. SAFETY AND TOLERABILITY ANALYSES

The safety analyses will be run on the Safety population. The analysis of safety in this study will include summaries of the following safety and tolerability data collected for each subject:

- Adverse Events
- Clinical Laboratory Investigations
- C-SSRS
- BDI-II
- Vital Signs
- Physical Examinations and examinations of the oral cavity

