11.5 Physical Examination and Oral Cavity Exam

A standard physical examination will be performed at Screening, Baseline, and Week 14. In addition, a separate examination of the oral cavity will be performed at each visit (Screening through Week 14). Oral cavity examination findings will be documented separately from other physical examination findings.

A data listing of the results at each scheduled visit will be presented for both the standard physical examination and the examination of the oral cavity.

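### Protocol 13.5 and SAP 11 promise summaries of oral cavity examination findings but specify only listings, so findings not recorded as adverse events are not tabulated by arm

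*Protocol*

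**What the plan says.** Protocol 13.5 opens its list of safety data with "The analysis of safety assessments in this study will include summaries of the following safety and tolerability data collected for each patient". One of the six items is "Changes from baseline in physical examination findings including examination of the oral cavity". Later in the same section the output is given: "Physical examination data and oral examination data will be presented in data listings".

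SAP 11 has a parallel lead-in, "The analysis of safety in this study will include summaries of the following safety and tolerability data collected for each subject", and its list includes "Physical Examinations and examinations of the oral cavity". The SAP item does not mention change from baseline. SAP 11.5 then says "A data listing of the results at each scheduled visit will be presented", for both the standard physical and the oral cavity examination. SAP 9.3 likewise specifies listings.

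The examination is a named safety endpoint in Protocol 7.2.4: "Assessment of physical examination findings including examinations of the oral cavity".

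Separately, Protocol 13.5 and SAP 11.1 plan tables of oral cavity TEAEs, overall, by severity, and by system organ class and preferred term. SAP 8.1 says that tables in general are by treatment group.

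**The concern.** The product is dissolved under the tongue, so local oral tolerability is the safety question specific to the formulation. SAP 11.1.3 gives the sublingual route as the reason for the oral examinations. Protocol 12.3.6 requires examiners trained and certified by the sponsor, with a thorough examination at Visit 1 and visual examinations at Visits 2 to 6.

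Of the six items in the Protocol 13.5 list, this is the only one with no summary of its own. At stake is whether the reader of the study report sees, by arm, how many patients developed a new or worsened oral finding on examination, or must count them from a listing. The adverse event tables cover part of this. The part they miss depends on what each site chose to record as an adverse event.

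**Working it through.** The point depends on no design figure, and the plan gives none to reproduce. The check is a reading of the text plus one count.

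**1. Promise against output in Protocol 13.5.**

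| Item under the summaries lead-in | Output defined later in 13.5 |
|---|---|
| Adverse events | Incidence tables, by severity and relationship |
| Laboratory tests | Descriptive values and changes, shift tables |
| Vital signs | Descriptive values and changes |
| C-SSRS | Counts by treatment group |
| BDI-II | Descriptive values and changes |
| Physical and oral cavity examination | Listing only |

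SAP 9.3 and 11.5 also give listings only. Neither document defines a table, shift or change-from-baseline output for oral examination findings.

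**2. How an examination finding reaches a by-arm table.** Protocol 12.3.1 has observed adverse events recorded on the CRF. SAP 11.1.3 says oral cavity adverse events may be ones observed during an oral examination, and identifies them by a yes answer to a CRF question. They then enter the oral cavity TEAE tables. The TEAE definitions in Protocol 14.1 and SAP 11.1 include pre-existing conditions that worsen. New and worsened lesions recorded as adverse events are therefore compared by arm.

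**3. What falls outside.** Protocol 11.3 to 11.5 have abnormalities described on the oral examination source document. For laboratory values, Protocol 12.3.7 says clinically significant abnormalities after Screening are recorded as adverse events. No matching rule exists for oral findings. A finding that a site does not record as an adverse event appears only in the listing.

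**4. Denominator.** SAP 8.1 generally uses the whole study population for percentages. Protocol 12.3.6 drops the examination at telephone visits. Protocol 11.5.1 allows it at Week 14/ET home visits only when a sponsor-certified clinician attends. A percentage of all patients would treat unexamined patients as free of findings.

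**5. Size.** Visit 2 is pre-dose and cannot show a new finding, so the scheduled post-baseline examinations are Visits 3, 4, 5 and 6. The maximum is 470 x 4 = 1,880, before losses to telephone visits, home visits without a certified clinician, and dropout.

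**6. Illustration only.** Suppose 235 patients per arm are all examined. The half-width of a 95% interval for the difference is 1.96 x sqrt[p0(1 - p0)/235 + p1(1 - p1)/235].

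- 2% against 6%: 1.96 x sqrt[(0.0196 + 0.0564)/235] = 0.035, so 4.0 points +/- 3.5.
- 2% against 8%: 1.96 x sqrt[(0.0196 + 0.0736)/235] = 0.039, so 6.0 points +/- 3.9.

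The rates are assumed and have no source in the documents. They show what a table of this size could resolve. They do not measure what is lost, because some of these findings would already be in the TEAE tables.

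**The case against.** The strongest reply is that oral tolerability already has dedicated by-arm tables. A reader might infer from the listing-only text that new oral lesions seen on examination are never compared between drug and placebo, or that the trial cannot answer its safety objective. The documents do not support either inference, because examination findings recorded as adverse events reach the oral cavity TEAE tables and worsening counts. Nor do they support the view that findings judged non-significant can never get there. The adverse event definition in Protocol 14.1 sets no threshold of clinical significance.

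It can also be said that both documents agree on listings, so the lead-ins are only loosely worded. SAP 11 does not promise change from baseline, and Protocol 7.2.4 speaks of assessment, not of incidence by arm. Protocol 11.2.2 recommends recording all Baseline oral findings "so that there is a complete and accurate baseline assessment available for comparison to findings at later visits". That is advice to sites on source records and can be read as helping the examiner compare within a patient; it does not promise a statistical comparison.

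These points limit the consequence but do not remove the mismatch. Protocol 13.5 does name change from baseline in oral findings as something to be summarised, and nothing delivers it. Deleting the promise would make the text consistent, but findings not recorded as adverse events would still be untabulated.

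It is also fair that a between-arm confidence interval and a breakdown by oral region would go further than the plan does for other safety data, and that nothing shows the CRF captures region.

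**Conclusion.** The inconsistency is confirmed in both documents. A named safety endpoint of a sublingual product has no by-arm summary of its own. By-arm comparison rests on oral cavity TEAEs, and examination findings not recorded as adverse events are not tabulated by arm.

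The consequence is limited. It touches neither the primary result nor the adverse event tables. The upper bound of 1,880 counts scheduled examinations, not missed findings. How many findings fall outside the TEAE tables depends on site practice and cannot be derived from the documents. The conclusion assumes that no separate document, such as table shells or CRF instructions, already defines an examination summary or a rule for turning oral findings into adverse events. This is a cheap improvement.

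**What to change.** In Protocol 13.5 and SAP 11.5, add one descriptive by-arm table for the Safety Population: the number and percentage of patients with at least one new or worsened oral cavity finding relative to Baseline (Visit 2), overall and by visit. Use patients actually examined as the denominator and show that number, because telephone visits, and Week 14/ET home visits without a certified clinician, have no oral examination. Keep the listings and the oral cavity TEAE tables. A breakdown by region and a between-arm confidence interval are optional and depend on how findings are captured.

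The cost is one extra table and a few lines of SAP text. The table draws on examination results already planned for listing. If those are free text, someone blinded to treatment must classify them as new, worsened or unchanged before database lock.
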